Obtaining written informed consent, and HIPAA authorization, will be conducted in English by trained study personnel either remotely, at the subjects' homes, or in the VAPORHCS Sleep Disorders Clinic or other outpatient clinics within the VAPORHCS and will not differ between subjects for any cohort. Prior to obtaining informed consent, subjects will be given a short screening questionnaire to ensure that they meet eligibility criteria. Study personnel will guide subjects step-by-step through the informed consent document and ensure subjects have had all questions answered. Subjects will be reminded several times that participation is entirely voluntary, and they are free to discontinue participation at any point, and likewise, investigators are free to discontinue their participation at any point.

Informed consent may also occur remotely via phone or video conferencing which will require that we collect the interested potential participant's name, phone number, email address, and physical mailing address prior to consent. Remote consent conversations will occur in one of the following ways:

- *DocuSign* – Study staff will initiate the sending of a DocuSign envelope to furnish the potential participant with links to the consent and authorization forms for conducting the consent conversation. These will be sent with approved template wording that reminds the volunteer not to sign anything until instructed to do so by the consenter during the scheduled phone or video visit. After the consent discussion the consenter will aid the subject in executing the documents and then in retrieving their copies of the fully executed consent and HIPAA Authorization for their records.

DocuSign will be used as the study's preferred method for fully remote HIPAA/Consent discussion. Choosing to use DocuSign will improve security and privacy for our research volunteers, will alleviate participants' burden in tracking and shipping these crucial study documents, and will help prevent the delays and errors that mail-in consent methods may encounter.

The study team has been approved by ORD for use of 350 envelopes (emails). Further details are located within the document 'Standard of Operating Procedure: DocuSign for Research'.

- **Mail-** (*This option will be used in cases where DocuSign is not feasible for any reason.*) Study staff will mail the consent form and HIPAA authorization form for the participant to review and then set up a meeting for study personnel to talk through the forms with the potential participant. Study personnel will go through each section of the consent form and HIPAA authorization form and address any questions the potential participant may have. If the subject agrees, they will be instructed to sign and date the forms and return them with the prepaid, pre-addressed envelopes provided. When the study team receives these forms, they will also sign and mail back the signed copy of the forms.

Risks and Side Effects:

The delivery of usual care is never altered by this study. Study risks include breach of confidentiality, psychological discomfort in completing study questionnaires, and mild physical discomfort from MBLT, and pain testing.

Psychological.

- **Questionnaires and Neuropsychological testing:** There is a small risk that completing questionnaires could be stressful, discomforting, or mildly embarrassing to the participants. The questionnaires take approximately ~30 min to complete. Since questions are asked about mood, including thoughts of self-harm and depression, there is a possibility that information about thoughts of suicide or evidence of depression will be gained that will require an intervention. How this information will be handled is discussed below in the *Suicidality* section.

Physical.

- **Morning Bright Light Therapy:** Light from a lightbox is essentially indistinguishable from natural light from the sun and consists of broad-spectrum white light. Morning bright light from a lightbox poses very minimal and rare risks. One study showed that light intensity of 10,000 lux received for an average of 40+ min per day over a five-year period had no major side effects. Minimal and uncommon side effects included eye irritation, irritability, headache, nausea, sensation of glare, dryness of eyes, and dryness of skin (as can occur from natural sunlight exposure). A rare occurrence of mania or rapid-cycling may occur in those with Bipolar Disorder due to too much exposure to bright light. For this reason, this study will exclude those with Bipolar Disorder. The manufacturer notes in the user guide that people with macular degeneration may be more at risk of retinal damage from blue light and should avoid it. Although the lightbox emits very little blue light, those with macular degeneration will be excluded from the study, as stated above in *Inclusion and Exclusion Criteria*. If problems are experienced, participants are free to stop the study at any time and/or call the Study Coordinator with any questions or issues.
- **Negative ion generator:** The negative ion generator will be modified so that it does not emit negative ions, so there will be no side effects from negative ions.
- **Actiwatch:** Participants may experience skin irritation from the actigraphy watch wristband, although very uncommon. Participants will be told to remove the actigraphy watch if this occurs. This would not exclude subjects from further participation.
- **Pressure algometer pain testing:** Pressure algometry has minimal risk for discomfort. Some studies, like this one, have the potential to cause "peripheral nerve stimulation." Peripheral nerve stimulation is a light touching sensation on the skin surface, lasting only for a few seconds. It may cause mild discomfort but is not harmful. There is a possibility that participants may experience some temporary redness or report some tenderness after the test. If at any point a participant expresses more than mild discomfort and/or wants to stop the test, we will stop.
- **Cold pressor pain testing.** The cold pressor test has minimal risk for discomfort. There is a possibility that participants may have some temporary redness or sensitivity after the test. If at any point a

participant expresses more than mild discomfort and/or wants to stop the test, they will be instructed to remove their hand from the ice bath. We will not allow the research subject to have their hand submerged for more than 5 minutes to prevent any tissue damage.

- Ischemic pain testing. The ischemic pain test has minimal risk for discomfort. There is a possibility that participants may have some temporary numbness or sensitivity after the test. If at any point a participant expresses more than mild discomfort and/or wants to stop the test, their blood pressure cuff will be immediately deflated.

Other.

- Because this study collects protected health information, there is always a risk of a breach of confidentiality. This risk is addressed below under *Privacy and Confidentiality*.

The possible benefits to the participants and to future understanding and improvements in delivery of sleep-related care to Veterans are reasonable and outweigh the risks of minor and rare physical harm, emotional distress, or breach of confidentiality to study participants.

Participant Safeguards:

This study will not include any vulnerable populations. Potential participants will be gauged for their interest in the study prior to being provided a consent form. Those participants that can verbally acknowledge understanding of the study and agree to participate will be consented by trained study personnel. If it appears that the subject is experiencing decisional impairment or an inability to understand the study, such as failing to repeat back the basic concepts of the study, that person will not be permitted to participate.

Suicidality:

In the event that a participant expresses the thought of harming themselves when they are at the clinic for the overnight sleep test, the sleep lab technician or the researcher, if present, will accompany them to the Emergency Department for a warm-transfer.

If during a follow-up phone call after the sleep test the volunteer expresses thoughts of harming themselves, then the researcher will contact the VA national crisis line at [contact] or [name] or the local suicide prevention line at [name] and connect the individual to that help by phone. In the event a direct phone transfer cannot be completed, then the researcher will ask that the participant remain available by phone. The researcher will provide the VA National Suicide Prevention Hotline with the name and phone of the participant and the VA Hotline will then phone the participant. The researcher will follow-up afterwards by phone to ensure that the participant has received adequate help and is safe.

In the event that questionnaire answers indicate depression or suicidality, their primary mental health provider will be notified. If they do not have a mental health provider, then their primary care physician will be notified to make a referral. If there is an immediate suicidal ideation, we will walk the participant to the emergency room for a warm transfer.

Benefits:

Participants may directly benefit from this study through the designated morning bright light. Outcomes include improved quality of sleep, an increase in quality of life, improved cognition, and reduction of pain. Subjects will receive modest monetary compensation for their time (see *Subject Compensation*).

Protected Health Information:

The following protected health information (PHI) will be collected in this study: full name, phone number, dates of research visits, date of birth, full mailing address, email address, and last four digits of the social security number. Demographics such as identified race & ethnicity will be collected and history regarding diagnosis of a sleep disorder; medical history will be confirmed or examined in chart and information regarding TBI, PTSD, and/or depression may also be collected. Information regarding drug and alcohol dependency will be examined for the purpose of determining eligibility to participate in the study and research personnel

involved in the study will not identify, directly or indirectly, any individual subject in any report of the research, or otherwise disclose the subject identities to anyone outside the IRB-approved VA personnel for this study in any manner (e.g. manuscript or publication). In addition, to create the GUID for Federal Interagency Traumatic Brain Injury (FITBIR) we will collect name at birth and place of birth (though note that no PHI/PII is ever disclosed to FITBIR). Data will be transferred to FITBIR.

At consent, a participant ID code will be assigned to each participant, and this will be used as the identifier for all further data collection. Research questionnaires will be collected on paper copies (all coded with the unique participant ID number and no identifiable data). The originals will be stored in a locked file cabinet in a locked office on the 4th floor of VAPORHCS building 101, room 432A. Original hardcopy consent and HIPAA forms will be stored in a locked drawer and office in building 101, room 432A. Electronic consents will be stored on the VAPORHCS limited-access Research drive. (R01:\Research\[name]\), on VA OneDrive and other future VA-approved platforms. In order to help facilitate remote visits, questionnaires may be mailed.

PHI that is mailed or transported between a home visit and the VA will also be coded and stored in the locked file cabinet upon receipt.

Prior to consent, first and last name and email address will be provided to DocuSign in order to initiate the electronic consent process. The consent to be used will also be relayed to DocuSign and, for this study, the consent will list the subject's status as a veteran who may have had a TBI, problems sleeping, problems with memory, and/or problems with pain. Please see "Letter_DocuSign Memo for PO" provided with this protocol for details regarding the National VA's decision to deem DocuSign secure and appropriate for e-consent. Screening phone scripts have been developed which include discussion of this transfer of information and ask potential participants permission for transfer. Mail or in person consent is offered as an alternative within these documents.

Resources Available:

There is office space available at the VAPORHCS Sleep Disorders Clinic (building 100-6C), and provided by Research Service (building 101, rooms 432A, 430, 404, and 533) with locked file drawers in a dedicated, locked room (101/432A). Testing will occur at the VAPORHCS at the aforementioned rooms available to the study team. The local VAPORHCS Co-Investigator, [name]., Ph.D., is a clinical provider in the Sleep Disorders Clinic.

Costs To Subjects:

Participants may incur a minor cost from operating the energy-efficient lightboxes or negative ion generators. The estimated electrical cost to power the lightbox amounts to <30 cents over the course of the study period. There are no other costs involved with participating in the study. Transportation for subsequent visits will not be provided or reimbursed by the study team.

Subject Compensation:

Subjects will receive compensation via gift cards or other cash equivalent. Each subject in each group (MBL or negative ion generator) will receive the same compensation (up to \$100 in total).

- Visit 2 = \$20
- Visit 3 = \$60
- Visit 4 = \$20

Privacy and Confidentiality:

All physical copies of study documents will be stored in a locked file in a locked room (Room 432A). All study related materials will be coded only by participant identification number. To protect privacy and confidentiality, the electronic master list of study participants and their unique study identification number will be stored on the VAPORHCS limited-access Research drive, the VA OneDrive and other future VA-

approved. These platforms will be protected by password access to the VA computer system. Only IRB-approved study personnel will have access to this file.

De-identified study data will be disclosed to and uploaded onto the FITBIR Informatics System. Participants will be identified by the FITBIR GUID, the key to which will be accessible only to the investigators. The information gathered during this study will be kept confidential to the extent that the law allows. The subjects will be informed that these results may be published for scientific purposes, provided their identity is not revealed.

PHI that is mailed or transported between a home visit and the VA will also be coded and stored in the locked file cabinet.

Information and/or Specimen Management

Study information will be located at the VAPORHCS. Information collected from symptom questionnaires at clinical intake will include PHI such as name, mailing address, and phone number on the cover page. Questionnaires will be collected on physical copies with no identifiable data and only a coded participant ID on the cover page. The original hard copy questionnaires, as well as original consent and authorization forms, will be stored in a locked file cabinet in a locked office on the 4th floor of VAPORHCS in building 101, room 432A.

The actigraphy watches will be used to collect actigraphy data and will contain sleep patterns, overall light intake, and overall activity levels. The actigraphy watch has no ability to transmit wirelessly and must be connected to a proprietary charging dock via USB read by proprietary software in order to retrieve the data. Data will be downloaded onto a password-protected OHSU computer containing said proprietary software for actigraphy devices. All actigraphy data downloaded from the actigraphy device is coded data; no PHI is associated with any of this downloaded data. Raw actigraphy data will be housed on the limited-access Research drive, VA OneDrive, and other future VA-approved platforms at VAPORHCS.

HOBOs will be attached to the lightboxes which will track when the lightbox is turned on or off. The HOBOs do not have the ability to transmit wirelessly and must be connected to a USB dock to retrieve data. Data will be downloaded onto a password-protected OHSU computer containing VA-approved software.

Data and Safety Monitoring Plan (DSMP)

Participant Safety

[name], the principal investigator will be responsible for complying with the reporting requirements. [name] is the Responsible Clinician on record and will be responsible for monitoring the safety of the study. Continuous, close monitoring of participant safety will include prompt and frequent reporting of safety data (i.e., adverse/serious adverse events) to the local site IRB and the VA. Serious adverse events will be reported to the local IRB, and the project officer within 48 hours of the time project staff become aware of the incident. It is unlikely that study outcomes will adversely affect the health or well-being of research participants in this experimental study. Participants are under usual care for all treatment they receive for their sleep complaint, in addition to the proposed study arms. If depression or risk of suicide are evident due to questionnaire data collected (e.g., question 9 on the PHQ-9), then the participant will be referred for follow-up. If a participant indicates thoughts of self-harm, then steps will be taken to protect and support the participant as described above in the sections on Suicidality and on Risks and Side Effects.

Data safety and management

Our team has extensive experience collecting and managing research data from Veterans. All research records will be maintained according to the current VA research retention schedule. Our current VA IRB-approved studies operate under a standard operating procedure with specific instructions for administration and entry of questionnaire data. Safeguards are in place to cross-check for duplicate or erroneous data.

Subjects will be assigned a unique subject code as soon as they are consented that will follow them through the study. Inclusion of personally identifiable patient information will be minimized, but some

personally identifiable data will be included to decrease errors and allow cross checking of information through, for example, medical chart review. Strict security measures will be used to protect the data, all of which meet or exceed HIPAA requirements. Personal identifiers will only be accessible to authorized study personnel for the purposes for which it was collected.

The goals of our data management system are to maintain data accuracy and security, and to ensure efficient access for monitoring and analysis. All study personnel doing data collection will be carefully trained in their tasks (i.e., collection methods, security, auditing and tracking, prevention and detection of intrusion, back-up and recovery, quality control, monitoring and reporting.

Step-by-Step Guidance on Conducting the Study

Recruit subjects from methods described in “Subject Identification/Recruitment” section

1. Complete Visit 1.
 - a. Obtain written and verbal informed consent and HIPAA authorization from subjects
2. Schedule time to return to the VAPORHCS for Visit 2.
3. Complete Visit 2.
 - a. Provide subjects with lightbox or disabled negative ion generator
 - b. Collect subjects initial questionnaire data, complete pain testing, provide study diary
 - c. Compensate subjects with up to \$20
4. Schedule time to return to the VAPORHCS for Visit 3.
5. Complete Visit 3.
 - a. Collect subjects post-study questionnaire packet and complete pain assessment.
 - b. Collect subjects actiwatch, lightbox or negative ion generator, and study diary
 - c. Compensate subjects with up to \$60
6. Schedule time to return to the VAPORHCS for Visit 4.
 - a. Collect subjects follow-up questionnaire packet and complete pain assessment.
 - b. Compensate subjects with up to \$20
7. Thank subjects for their participation.

References & Literature Cited:

1. Centers for Disease and Control. Injury Prevention and Control: Traumatic Brain Injury and Concussion [Internet]. 2016. Available from: http://www.cdc.gov/traumaticbraininjury/get_the_facts.html
3. Okie S. Traumatic brain injury in the war zone. *N Engl J Med* 2005;352:2043–7.
4. Ouellet M-C, Savard J, Morin CM. Insomnia following Traumatic Brain Injury: A Review. *Neurorehabil Neural Repair* 2004;18(4):187–98.

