This proposal aims to apply a sleep intervention to improve chronic pain in Veterans with TBI. We propose to use morning bright light therapy (MBLT), a readily deployable, cost-effective, non-pharmacologic, and home-based sleep intervention, to improve sleep-wake disturbances and therefore ameliorate chronic pain and improve quality of life in Veterans with TBI. There is substantial scientific precedent for MBLT to be effective in improving sleep quality, as outlined by a recent meta-analysis of 53 MBLT-based studies.³¹ Indeed, the potential of MBLT to improve sleep quality in Veterans with TBI remains unexplored, and yet, highly promising. Outcomes will be assessed pre- and post-intervention, and at a 3-month follow-up time point. *Our central hypothesis is that MBLT will improve sleep quality and ameliorate pain, resulting in improved quality of life in Veterans with TBI.*

Specific Aim 1: Determine the effect of MBLT on *sleep quality* in Veterans with TBI.

- Hypothesis: Self-reported sleep quality, and sleep efficiency using actigraphy, will improve following 4-weeks of MBLT compared to sham in Veterans with TBI.

Specific Aim 2: Determine the effect of MBLT on *pain* in Veterans with TBI.

- Hypothesis: Self-reported pain, and pain testing via pressure algometry, will improve following 4-weeks of MBLT compared to sham in Veterans with TBI.

Specific Aim 3: Determine the effect of MBLT on *quality of life* in Veterans with TBI.

- Hypothesis: Self-reported quality of life will improve following 4-weeks of MBLT compared to sham in Veterans with TBI.

Scientific Rationale and Significance:

Sleep-Wake Disturbances Following TBI. It is nearly universally accepted that one of the principal complicating factors associated with TBI is sleep-wake disturbances. The functional and economic impact of sleep disturbances is staggering¹⁸ and well-known to *directly impair quality of life*,¹¹ preclude independent functioning, reintegration into civilian life, return to duty or success in vocational endeavors.

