Title: *Morning bright light to improve sleep quality in Veterans*

Publications:

Data collection ongoing.

Relevance:

This protocol has recruited 91 participants over 18 months, 60 of which underwent MBLT for 4 weeks. The primary purpose of this protocol was to assess feasibility outcomes, including recruitment rate, retention rate, and adherence to the light therapy. Of the participants with TBI, 88% of subjects remained adherent to light therapy for the full 4 weeks. Overall, 91% of subjects said they liked using the lightbox. We additionally found that MBLT improves self-reported sleep, mood, and quality of life in our pilot cohort, however, this study lacks a placebo device for comparison.

Research Design and Methods:

Veterans within the VA Portland Healthcare System (VAPORHCS) and non-Veterans will be recruited for participation in this study. This study will consist of at least 4 visits over the span of ~5-6 mo.

Study Overview and Timeline.

	Visit 1	Visit 2	At Home	Visit 3	Visit 4 Follow up
Time point:	Day 0	Week 2	Week 2-6	Week 6	Week 10
Informed consent	X				
Subject given actiwatch		X		X	
Conduct pain assessment		X		X	X
Subject given lightbox or sham		X			
Questionnaires		X		X	X
Daily use of intervention for 1 hour			X		
Total time	~120 min	~120 min	28 hours	~120 min	~120 min

- *Informed consent and HIPAA authorization.* Written and verbal informed consent will be obtained before all other Visit 1 activities and may take place on an earlier date if DocuSign is able to be used to facilitate the consent conversation.
 - In cases where DocuSign is not feasible, consent conversations will take place in office space available at the VAPORHCS Sleep Disorders Clinic (building 100-6C), in related outpatient clinical space, or in Research Service space approved for human subjects use

(building 101, rooms 432A, 430, 404), or in subjects' homes. Alternatively, consent may take place remotely via phone or video conferencing via mailed documents.

- Where DocuSign is feasible, study staff will initiate email of a DocuSign envelope providing subjects access to the consent and authorization forms ahead of the consent discussion. Subjects will then be guided through downloading the fully executed consent form.

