- Participants will be asked to fill out demographics information which will include their name (including name at birth), date of birth, city/town of birth, email and physical address, phone number, health history, and military history.
- Individuals without a medical record at the VA will be asked permission for study staff to request their medical record pertaining to sleep and traumatic brain injury.

Visit 2

- Visit 2 will occur ~2 weeks after visit 1. It can take place within the VAPORHCS Sleep Disorders Clinic (building 100-6C), in Research Service (building 101, rooms 432A, 430, 404, and 533), remotely via phone/video conferencing, or at the subject's home.
- *Questionnaires.* Subjects will complete baseline questionnaires. They take ~30 min to complete and include past medical history and self-reported measures on sleep, social habits, quality of life, mental health, pain, and other metrics related to subject's prior trauma exposure history. All questionnaires are validated and will be completed via pen and paper. Medical history and testing related to sleep will be accessed from the participants' VA medical records by study staff with VA credentials. Subjects may elect to complete these questionnaires at either this or subsequent visits as needed. Questionnaires may be mailed if completed remotely.
- *Equipment.* Subjects will be randomized to receive a lightbox (LightPad mini, Aurora Light Solutions) or sham-control modified negative ion generator. Devices will be modified by completely disconnecting the electrical wiring required for negative ion generation. This will be verified using a voltmeter. A small fan may be installed to emit a low humming noise as an indicator of activity. They will be instructed to use either device for 60 min every morning after waking up starting 2 weeks following this visit and continuing for 4 weeks. Light sensitive devices, called HOBOs, will be attached to the lightboxes which will track when the lightbox is turned on or off, as a secondary measure of light delivery.

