- *Pain testing.* Ischemic Pain Test. Ischemic pain testing may be used at VAPORHCS and at visits that are conducted remotely. This test will consist of a manual blood pressure cuff that is placed on the subject's non-dominant upper arm and inflated to 300 mmHg. Threshold will be determined by the amount of time that the subject perceives the constriction as mildly painful. Tolerance will be determined by the amount of time that the subject allows the constriction to continue. This will be done during a single trial. The upper limit of allowing the hand the constriction is 5 minutes.
- *Department of Defense Head Trauma Events Checklist (DoD HTEC).* Determination of TBI status occur through a semi-structured diagnostic interview following the DoD HTEC guidelines. This interview will take ~15 min to complete.
- *Reimbursement.* Subjects will be compensated with up to \$20

Visit 3

- Visit 3 will occur ~4 weeks after Visit 2 and will take place within the VAPORHCS Sleep Disorders Clinic (building 100-6C), in Research Service (building 101, rooms 432A, 430, 404, and 533), remotely via phone/video conferencing, or at the subject's home.
- *Measures.* The same series of questionnaires and pain testing conducted at Visit 1 will be repeated.
- *Equipment.* Subjects will return all equipment, including the actiwatch, lightbox and/or sham device.
- *Reimbursement.* Subjects will be compensated with up to \$60

Visit 4

- Visit 4 will occur ~4 weeks after Visit 3 and will take place within the VAPORHCS Sleep Disorders Clinic (building 100-6C), in Research Service (building 101, rooms 432A, 430, 404, and 533), remotely via phone/video conferencing, or at the subject's home.
- *Measures.* The same series of questionnaires and pain testing conducted at Visit 1 will be repeated.
- *Reimbursement.* Subjects will be compensated with up to \$20
- *End of study debrief.* Subjects will be debriefed about our experimental design, given the inclusion of a placebo-controlled condition. We will provide subjects with a written description that we will describe to them in person and address any questions they may have.

Mailed forms and equipment. In an effort to reduce subject's time at the Portland VA we may mail consent forms, questionnaires, equipment and pre-addressed, pre-paid return envelopes directly to their homes. Instructions will be provided via phone or video conferencing.

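### The 3-month follow-up, the 5-6 month span and the device start date contradict a visit schedule that ends at Week 10

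*Protocol*

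**What the plan says.** Four parts of the Protocol fix the calendar.

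- **Specific Aims/Purpose.** "Outcomes will be assessed pre- and post-intervention, and at a 3-month follow-up time point". The origin of the 3 months is not given. The hypotheses of all three aims are set after four weeks of treatment; Aim 3, for example, reads "Self-reported quality of life will improve following 4-weeks of MBLT compared to sham in Veterans with TBI".
- **Research Design and Methods, opening paragraph.** "This study will consist of at least 4 visits over the span of ~5-6 mo".
- **Study Overview and Timeline (table).** Visit 1 is at Day 0, Visit 2 at Week 2, Visit 3 at Week 6 and the Visit 4 follow-up at Week 10. Home use of the device occupies Weeks 2 to 6, totalling 28 hours.
- **Visit texts.** "Visit 2 will occur ~2 weeks after visit 1"; "Visit 3 will occur ~4 weeks after Visit 2"; "Visit 4 will occur ~4 weeks after Visit 3". Under Visit 2, Equipment, either device is to be used for an hour each morning, "starting 2 weeks following this visit and continuing for 4 weeks". Under Visit 3, Equipment: "Subjects will return all equipment, including the actiwatch, lightbox and/or sham device".

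The end-of-study debrief takes place at Visit 4, and the Step-by-Step Guidance finishes with that visit.

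**The concern.** One schedule is written out, and three statements contradict it: the follow-up interval, the total span and the start of device use. Two things are at stake.

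**Follow-up.** If the schedule is followed, no 3-month outcome is collected. A Visit 4 result reported under the wording of the Aims would claim longer persistence of effect than was observed.

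**Post-treatment comparison.** Each hypothesis concerns the state after four weeks of light therapy against sham. If staff apply the start instruction in the Visit 2 text and still hold Visit 3 about four weeks after Visit 2, the post-treatment measures fall at the midpoint of the course and the device goes back with half of it unused. If staff read the instructions differently from one participant to the next, exposure at Visit 3 would vary within each arm.

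**Working it through.** **Conversion.** One month = 365.25 / 12 / 7 = 4.348 weeks, so 3 months = 13.0 weeks, 5 months = 21.7 weeks and 6 months = 26.1 weeks.

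**Reproducing the schedule.** The intervals in the visit texts give 0 + 2 = Week 2 (Visit 2), 2 + 4 = Week 6 (Visit 3) and 6 + 4 = Week 10 (Visit 4). This matches the table exactly. Week 10 is 10 / 4.348 = 2.3 months. The table's device time also reproduces: 4 weeks × 7 days × 1 hour = 28 hours.

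**Device use under the Visit 2 text.** The start is Week 2 + 2 = Week 4 and the end is Week 4 + 4 = Week 8. The table says Weeks 2 to 6.

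**Is Visit 4 a 3-month point from any origin?**

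| Origin | Week of origin | Visit 4 falls after | Short of 13 weeks by | A 3-month point would fall at |
|---|---|---|---|---|
| Day 0 (consent) | 0 | 10 weeks | 3 weeks | Week 13 |
| Visit 2 | 2 | 8 weeks | 5 weeks | Week 15 |
| Visit 3, or end of use per the table | 6 | 4 weeks | 9 weeks | Week 19 |
| End of use per the Visit 2 text | 8 | 2 weeks | 11 weeks | Week 21 |

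None does. Counting 3 months as 12 weeks shortens each shortfall by one week and changes nothing.

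**Total span.** The written schedule is 21.7 − 10 = 11.7 weeks below the lower end of the stated span. If the three conflicting statements are combined, with follow-up counted from the end of use, the total is 2 + 2 + 4 + 13 = 21 weeks (4.8 months). That is 0.7 week under 5 months, so those statements roughly fit one another and do not fit the schedule. The 21 weeks is derived here; the Protocol does not print it.

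**Exposure at Visit 3 under the Visit 2 text.** Week 6 − Week 4 = 2 weeks, which is 14 sessions of 1 hour. 14 / 28 = 50% of the planned use, as an upper limit with perfect adherence. Under the table it is 4 weeks and 28 hours.

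**Could another contact supply the 3-month outcome?** The calls described under Phone calls do ask about sleep, pain and quality of life. They are made when needed between visits, are not tied to a date and cannot include pain testing. No later visit is scheduled.

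**The case against.** The strongest reply is that the Protocol contains only one worked-out calendar. The table, visit intervals, Weeks 2-6 of use, 28 hours and device return at Visit 3 all agree. The 21-week alternative has to be assembled from scattered statements and needs an assumed origin; counted from Visit 3 the follow-up would be at Week 19. The span is given as approximate, four visits are a minimum, and consent may be taken earlier than Visit 1. The mid-course Visit 3 arises only if the Visit 2 start instruction is mixed with the scheduled Visit 3. Finally, no hypothesis concerns durability.

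Much of this is fair as to framing. The 21 weeks is a derived figure, the mid-course problem is conditional, and Day 0 and Visit 2 are weak origins for a follow-up named after the post-intervention assessment. The overstatement of durability would occur only if Week 10 results were reported as 3-month results.

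None of it removes the contradiction. Approximate wording does not stretch 4 weeks to 13, or 10 weeks to nearly 22. Earlier consent lengthens participation but does not move Visit 4 relative to treatment. Permission for further visits does not schedule one. The start instruction is operative text for staff and participants, and a statistical analysis plan cannot restore sessions lost when a device is returned early.

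**Conclusion.** The point holds. Visit 4 is at Week 10, 4 weeks after Visit 3 (or 2 weeks after the end of use as the Visit 2 text has it), against about 13 weeks for the follow-up announced in the Aims. The scheduled visits cover 2.3 months, less than half of the stated 5-6. Separately, the start of device use is given in two ways that differ by two weeks. Under one of them Visit 3 could fall after at most 14 of the 28 hours, which could affect the comparison behind all three hypotheses.

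Confidence is high that the passages conflict. Nothing in the document shows which timing is intended, and no position is taken on that. The figures rest on the stated intervals taken at face value, daily one-hour use and 4.348 weeks per month. This should be corrected; it is not fatal to the design.

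**What to change.** Reconcile Specific Aims/Purpose, the span statement and table in Research Design and Methods, and the Visit 2, 3 and 4 texts to a single calendar in which device start, end of use, device return, Visit 3 and Visit 4 agree. State the follow-up interval together with its origin, and make the total span match.

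- If Week 10 stands, the Aims must stop calling it a 3-month follow-up. The cost is a narrower statement about persistence of effect.
- If 3 months is intended, the Visit 4 schedule must change to match. That moves it 3 to 11 weeks later (Week 13 to Week 21, depending on the origin) and lengthens participation.

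For participants already seen, report Visit 4 by the interval observed, and describe from the study diaries (and, for lightboxes, the attached loggers) how much use preceded Visit 3.

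The same amendment should settle two neighbouring inconsistencies. The actigraphy watch is to be worn throughout the study, yet the Visit 3 text has it returned while the table marks it as given at that visit. Visits 3 and 4 are said to repeat measures from Visit 1, although the baseline questionnaires and pain tests are at Visit 2.

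Apart from a possible later Visit 4, the cost is an amendment to the text.
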